2.7.1 Adverse events (AEs)

The crude incidence of treatment-emergent adverse events (i.e., events started after the first dose of study treatment or events present prior to the first dose of study treatment but increased in severity based on preferred term and on or before last dose + 84 days) will be summarized by primary system organ class and preferred term. Confidence intervals for the crude rate will be derived as described in Section 5.5.2. In addition, exposure time-adjusted incidence rates including 95% confidence intervals will be provided for the entire treatment period (See [Section 5.5.3](#)). A graphical display of the crude incidence rates and exposure-adjusted rates will be presented for all AEs and serious AEs by system organ class.

Adverse events reported will be presented in descending frequency according to its incidence in total secukinumab group (combining all secukinumab treatment groups) starting from the most common event. Summaries (crude incidences only) will also be presented for AEs by severity and for study treatment related AEs. If a particular AE 'severity' is missing, this variable will be listed as missing and treated as missing in summaries. If a subject reported more than one adverse event with the same preferred term, the adverse event with the greatest severity will be presented. If a subject reported more than one adverse event within the same primary system organ class, the subject will be counted only once with the greatest severity at the system organ class level, where applicable.

Separate summaries will be provided for death, serious adverse event, other significant adverse events leading to discontinuation and adverse events leading to dose adjustment (including study treatment discontinuation).

A graphical display of relative frequencies within system organ classes and relative risks, as appropriate, will be presented.

Adverse events will also be reported separately by Standardized MedDRA Query (SMQ) according to MedDRA. The MedDRA version 26.1 will be used for reporting. Non-treatment emergent adverse events will be listed.

For SAEs occurred during screening a listing will be prepared for all subjects screened including screening failures.

The safety analysis that will be performed for treatment emergent AEs and on treatment labs and vital signs for each analysis period is described in Table 2-3.

Algorithms for date imputations will be provided in Programming Datasets Specification.

Table 2-3 Overview of analysis on some safety endpoints

| Analysis period | AEs & SAEs | AEs-SMQ | AEs by severity | study drug related AEs | Notables for (vitals/ECG), lab criteria | Risk |
|------------------|--|-------------------------------|-------------------|------------------------|---|--|
| Day 1 – Week 16 | • crude incidence | • crude incidence | • crude incidence | • crude incidence | • crude incidence | • crude incidence |
| Entire Treatment | • crude incidence • exp.time adjusted incidence | • exp.time adjusted incidence | • crude incidence | • crude incidence | • crude incidence | • crude incidence • exp.time adjusted incidence |

* Exposure-adjusted incidence rates will be done for the following:

- At the PSOC for AE and SAE
- At the PT level for common AEs, which is defined as at least 2% of the patients in the secukinumab during the initial treatment period (i.e. up to week 16) or events that had an incidence rate of at least 5.0 cases per 100 subject-years in the combined secukinumab groups during the entire treatment period
- At Level 1 for Risks and SMQ analyses

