2.1 Data analysis general information

The primary endpoint analysis will be performed after all participants complete Week 16 or discontinued earlier and the final analysis will be conducted on all participant data at the time the study ends, both by Novartis. Any data analysis carried out independently by the investigator should be submitted to Novartis before publication or presentation.

Novartis will perform the analysis at Week 16 and final analysis. Statistical software SAS version 9.4 or later will be used.

Summary statistics for continuous variables will generally include the number of participants (N), minimum, lower quartile, mean, standard deviation (SD), median, upper quartile, and maximum. For binary or discrete variables, the absolute number of participants in each category and relative frequencies will be provided.

Unless otherwise specified, two-sided 95% confidence intervals will be displayed.

In case of a global health disruptive event, such as pandemic/epidemic (e.g., COVID-19), affecting the ability of the patient or the site to adhere to protocol requirements and assessments and therefore leading to a potential increase in the number of missing measurements, additional analysis populations may be defined as per the instructions and procedures outlined in Section 16.9 in the protocol.

The efficacy evaluation of secukinumab relative to placebo will generally focus on the first 16 weeks of treatment unless otherwise specified.

Data analysis will be presented by treatment group. Efficacy and safety data for the 16-week placebo-controlled period and the entire treatment period as appropriate will be presented by the following two treatment groups. Participants may be included in more than one treatment group for some analysis (e.g. exposure adjusted adverse events over the entire treatment period).

These treatment groups represent the regimens to which participants will be eligible to be randomized:

- Secukinumab 150 mg regimen
- Placebo regimen

Note that the treatment groups above for a participant may differ depending on the time period of the analysis and whether one assesses the participant for efficacy or safety.

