2.1.1 General definitions

2.1.1.1 Treatment groups

The summaries by treatment will be performed by the randomized treatment or treatment sequence.

- Randomized treatment:
 - AIN457 150 mg s.c.
 - Placebo s.c.
- Treatment sequence:
 - AIN457 150 mg
 - AIN457 150 mg – AIN457 300 mg
 - Placebo
 - Placebo – AIN457 150 mg
 - Placebo – AIN457 150 mg – AIN457 300 mg

For some safety summaries (e.g. exposure-adjusted) the ‘switch’ treatment may be summarized separately:

Week 1 – Week 16: AIN457 150 mg, Placebo

Entire study: Any AIN457 150 mg, Any AIN457 300 mg, Any AIN457, Placebo

Unless otherwise specified, at the primary endpoint analysis, efficacy data for the placebo-controlled period and safety data up to Week 16 and Entire study will be presented. Additional aspects of efficacy, safety and tolerability of secukinumab will be investigated in the final analysis. Additional analyses may also be performed to support interactions with health authorities, as necessary.

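### Over the entire treatment period, AEs by severity, related AEs and notable abnormalities get crude incidence only, so any placebo comparison in those three tables is confounded by exposure or diluted by the switch

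*SAP*

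**What the plan says.** SAP 2.7.1 sets the rule for two categories: "Summaries (crude incidences only) will also be presented for AEs by severity and for study treatment related AEs". For AEs in general the same section promises more: "exposure time-adjusted incidence rates including 95% confidence intervals will be provided for the entire treatment period".

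Table 2-3 carries this through by analysis period. Reading its Entire Treatment row from the SMQ column to the risk column gives "exp.time adjusted incidence | • crude incidence | • crude incidence | • crude incidence | • crude incidence • exp.time adjusted incidence". SMQs therefore get the adjusted rate, risks get both measures, and the three columns between them (severity, study-drug relatedness, notable vitals, ECG and laboratory values) get crude incidence alone. AEs and SAEs, in the column before SMQs, get both. The footnote lists where adjusted rates are produced, starting with "At the PSOC for AE and SAE", then common preferred terms, then Level 1 for risks and SMQs. Severity, relatedness and notables are not listed.

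The SAP offers two column layouts for entire-period safety data. SAP 2.1.1.1 permits, for some summaries, "Entire study: Any AIN457 150 mg, Any AIN457 300 mg, Any AIN457, Placebo". SAP 2.1 says that data for "the entire treatment period as appropriate will be presented by the following two treatment groups", meaning the secukinumab 150 mg and placebo regimens. Neither section says which layout the three crude tables will use.

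Protocol 12.5.2 provides exposure-adjusted AE incidence only where appropriate, with no commitment for these categories.

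**The concern.** All placebo participants move to secukinumab at Week 16, while secukinumab dosing runs to Week 48 with 12 weeks of follow-up. A crude percentage has participants as its denominator and takes no account of how long each was observed. When one column is observed for much longer than the other, the crude percentages differ even if the drug does nothing.

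At stake is how severe AEs, related AEs and notable values read in the entire-period tables. SAP 2.1.1.1 presents entire-study safety data at the primary endpoint analysis as well as at the end, and SAP 2.14 says the primary endpoint analysis is for regulatory submission. Nothing in the SAP warns against comparing these columns with placebo.

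**Working it through.** **Planned duration.** Protocol 6.1.4 gives 60 weeks with the last dose at Week 48. This reproduces: 16 + 44 = 60 weeks, and Week 48 + 84 days (12 weeks) = Week 60.

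**Inputs.** 134 participants randomized 1:1, so 67 per arm (SAP 1.1). Exposure ends at the treatment switch, or at the earlier of last dose + 84 days and last visit; switchers count under both treatments (SAP 2.4.1). I assume no dropout, because the documents give no rate.

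**Exposure, Any AIN457 against Placebo.**
- Placebo: 16 weeks.
- Secukinumab: 60 weeks if randomized to it, 60 − 16 = 44 weeks for switchers.
- Mean per participant: (60 + 44)/2 = 52 weeks; 52/16 = 3.25. Counted only to Week 52: (52 + 36)/2 = 44; 44/16 = 2.75.
- Total person-time: 67 × (60 + 44) = 6,968 against 67 × 16 = 1,072 participant-weeks, ratio 6.5.

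The per-participant figure is the relevant one for a crude percentage. It applies to completed follow-up. At the primary endpoint analysis it will be lower, by an amount that depends on accrual.

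**Spurious ratio for severity and relatedness.** Assume the same constant hazard on both treatments and a 16-week placebo incidence i. Incidence over w weeks is 1 − (1 − i)^(w/16), with exponents 60/16 = 3.75 and 44/16 = 2.75.
- i = 5%: 17.5% and 13.2%, mean 15.3%, ratio 3.1.
- i = 10%: 32.6% and 25.2%, mean 28.9%, ratio 2.9.
- i = 20%: 56.7% and 45.9%, mean 51.3%, ratio 2.6.

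For very common events the ratio shrinks as both columns fill up. At an assumed 2 first events per subject-year it is 85.7% against 45.8%, or 1.87.

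**What adjustment does.** SAP 5.5.3 estimates the rate as D/T (participants with an event over time at risk). At an assumed 0.5 first events per subject-year, both columns have an expected rate of 50 per 100 subject-years. Crude incidence would be 39.1% against 14.2%, ratio 2.75.

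**Notable abnormalities.** These are found only when measured, so I count the analysis visits in SAP Table 2-1, leaving out Week 60, which has no window there.
- Hematology and chemistry: 5 through Week 16 (Weeks 1, 2, 4, 12, 16), then 4. Any AIN457 mean (9 + 4)/2 = 6.5; 6.5/5 = 1.3.
- Vital signs: 7 through Week 16, then 9. Mean (16 + 9)/2 = 12.5; 12.5/7 = 1.8.
- ECG: Weeks 16 and 52. Mean (2 + 1)/2 = 1.5; 1.5/1 = 1.5.

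**Randomized-regimen layout.** Both columns have 60 planned weeks, so no exposure artefact arises. In the placebo column, 44/60 = 73% of the follow-up is on open-label secukinumab, which pulls the two columns together.

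**The case against.** The plan already contains a fair comparison. Table 2-3 gives crude incidence for all three categories over Day 1–Week 16, where allocation is randomized and planned exposure equal. Over the entire period, AEs, SAEs, SMQs and risks do get adjusted rates. SAP 2.7 plans no formal safety testing. All of this stands, and it confines the problem to placebo comparisons in three descriptive tables. A reader might infer that safety signals cannot be told from longer observation anywhere in this plan; the documents do not support that.

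The columns that create the 3.25-fold difference are optional. SAP 2.1.1.1 only permits them, and its example is exposure-adjusted summaries. This stands too, so the layout is an assumption here. A reader might also infer that the comparison is uninterpretable under either layout. It is not: by randomized regimen it is a well-defined contrast of two sequences with equal follow-up, though diluted as a comparison with placebo.

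A third tempting reading is that notable values would also look about three times as frequent. The visit counts above do not support it.

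A fourth is that relative risks are planned for these tables. The only sentence on the subject is "A graphical display of relative frequencies within system organ classes and relative risks, as appropriate, will be presented". It names no period and none of the three categories.

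Finally, the remedy is partial. The adjusted rate assumes constant intensity. From Week 16 investigators know that everyone is on active drug, which can shift relatedness judgements in a way no exposure adjustment removes.

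**Conclusion.** The point holds as a limited one. The text of SAP 2.7.1 and Table 2-3 agree that these three entire-period tables are crude only, with no reason given for treating them differently from the rest of the row.

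Under the Any AIN457 and Placebo columns, a placebo comparison of severity or relatedness would be inflated about 2.6 to 3.1 times with no drug effect. That rests on the column layout, equal constant hazards, no dropout, completed follow-up and 16-week placebo incidences of 20% to 5%. For notables only the assessment opportunity is unequal, by about 1.3 to 1.8. Under the randomized-regimen columns the problem is dilution.

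The Day 1–Week 16 tables are unaffected, and crude percentages within the secukinumab columns remain valid description. It is the entire-period crude comparison with placebo that should not be read at face value.

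**What to change.** In SAP Table 2-3, choose one of two changes for the Entire Treatment row:
- add exposure-adjusted rates by the SAP 5.5.3 method for AEs by severity and for study-drug-related AEs, and amend the crude-only sentence in 2.7.1 to match; or
- show the entire-period crude tables for severity, relatedness and notables for secukinumab columns only.

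Under either option, state that crude comparisons with placebo for these categories, and any relative-risk display, are limited to Day 1–Week 16.

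The cost is a table and text edit plus slightly more output. The estimator is already defined, and SAP Table 5-3 already works an example for a placebo participant who switches to 150 mg. If adjusted rates are added, note beside them that they assume a constant hazard and do not correct for open-label judgement of relatedness after Week 16.

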2.7.1.1 Adverse events of special interest / grouping of AEs

Safety topics of interest, including risks defined in the Risk Management Plan (RMP) or other topics of interest for signal detection or routine safety analysis can be retrieved via the RMP flag and SPP flag. The crude incidence and exposure-adjusted incidence rates for the safety topics of interest will be summarized.

2.7.2 Deaths

Separate summaries will be provided for deaths.

2.7.3 Laboratory data

The summary of lab data will only include treatment emergent data, which are defined as those lab assessments after the first dose of study treatment and on or before last dose +84 days.

Reported laboratory assessments with either a less than or greater than sign (“<” or “>”) will be used for analysis after removal of the sign and conversion to standard unit. These laboratory data will be displayed in listings using the standard unit with the reported sign (“<” or “>”).

The summary of laboratory evaluations will be presented for three groups of laboratory tests (hematology, serum chemistry and urinalysis).

For urinalysis, frequency tables will be presented.

Descriptive summary statistics for the change from baseline to each study visit will be presented. These descriptive summaries will be presented by test group, laboratory test and treatment group. Change from baseline will only be summarized for participants with both baseline and post baseline and will be calculated as:

Change from baseline = post baseline value – baseline value

For each parameter, the maximum change from baseline within each study period will be evaluated analogously.

In addition, shift tables will be provided for all parameters to compare a participant's baseline laboratory evaluation relative to the visit's observed value. For the shift tables, the normal laboratory ranges will be used to evaluate whether a particular laboratory test value was normal, low, or high for each visit value relative to whether the baseline value was normal, low, or high. These summaries will be presented by laboratory test and treatment group. Shifts will be presented by visit as well as for most extreme values post-baseline. These summaries will be presented by laboratory test and treatment group.

The following laboratory parameters will be analyzed with respect to numerical Common Terminology Criteria for Adverse Events (CTCAE) grades, given in: hemoglobin, platelets, white blood cell count, neutrophils, lymphocytes, creatinine, total bilirubin (TBL), gamma-glutamyl transferase (GGT), alanine aminotransferase (ALT), aspartate aminotransferase (AST), alkaline phosphatase (ALP), glucose, cholesterol, triglycerides (TG).

These summaries will be split into hematology and chemistry for study level reports and the pooled summary of clinical safety.

Table 2-4 CTCAE grades for laboratory parameters to be analyzed

| CTCAE v4.03 Term | Grade 1 | Grade 2 | Grade 3 | Grade 4 |
|-------------------------------|--|---|--------------------------------------|---|
| HGB decreased (Anemia) | <LLN - 100 g/L | <100 - 80 g/L | <80 g/L | Life-threatening consequences; urgent intervention |
| Platelet count decreased | <LLN - 75.0 x10e9 /L | <75.0 - 50.0 x10e9 /L | <50.0 - 25.0 x10e9 /L | <25.0 x 10e9 /L |
| White blood cell decreased | <LLN - 3.0 x 10e9 /L | <3.0 - 2.0 x 10e9 /L | <2.0 - 1.0 x 10e9 /L | <1.0 x 10e9 /L |
| Neutrophil count decreased | <LLN - 1.5 x 10e9 /L | <1.5 - 1.0 x 10e9 /L | <1.0 - 0.5 x 10e9 /L | <0.5 x 10e9 /L |
| Lymphocyte count decreased | <LLN - 0.8 x 10e9/L | <0.8 - 0.5 x 10e9 /L | <0.5 - 0.2 x 10e9 /L | <0.2 x 10e9 /L |
| Creatinine increased* | >1 - 1.5 x baseline; >ULN - 1.5 x ULN | >1.5 - 3.0 x baseline; >1.5 - 3.0 x ULN | >3.0 x baseline; >3.0 - 6.0 x ULN | >6.0 x ULN |
| TBL increased | >ULN - 1.5 x ULN | >1.5 - 3.0 x ULN | >3.0 - 10.0 x ULN | >10.0 x ULN |
| GGT increased | >ULN - 2.5 x ULN | >2.5 - 5.0 x ULN | >5.0 - 20.0 x ULN | >20.0 x ULN |

| CTCAE v4.03 Term | Grade 1 | Grade 2 | Grade 3 | Grade 4 |
|--------------------------------------|--------------------|------------------------------------|-------------------------------------|---------------|
| ALT increased | >ULN - 3.0 x ULN | >3.0 - 5.0 x ULN | >5.0 - 20.0 x ULN | >20.0 x ULN |
| AST increased | >ULN - 3.0 x ULN | >3.0 - 5.0 x ULN | >5.0 - 20.0 x ULN | >20.0 x ULN |
| ALP increased | >ULN - 2.5 x ULN | >2.5 - 5.0 x ULN | >5.0 - 20.0 x ULN | >20.0 x ULN |
| Glucose increased (Hyperglycemia) | >ULN - 8.9 mmol/L | >8.9 - 13.9 mmol/L | >13.9 - 27.8 mmol/L | >27.8 mmol/L |
| Glucose decreased (Hypoglycemia) | <LLN - 3.0 mmol/L | <3.0 - 2.2 mmol/L >7.75 - 10.34 | <2.2 - 1.7 mmol/L >10.34 - 12.92 | <1.7 mmol/L |
| Cholesterol high | >ULN - 7.75 mmol/L | mmol/L | mmol/L | >12.92 mmol/L |
| Hypertriglyceridemia | 1.71 - 3.42 mmol/L | >3.42 - 5.7mmol/L | >5.7 - 11.4 mmol/L | >11.4 mmol/L |

* Note: for "creatinine increased" the baseline criteria do not apply

Shift tables will be presented comparing baseline laboratory result (CTCAE grade) with the worst results (expressed in CTCAE grade) during the treatment phase (either initial up to week 16 or entire) analyzed. Of note, baseline will be defined as last assessment prior to first dosing in initial treatment phase.

Summaries for newly occurring or worsening clinically notable lipid abnormalities will also be provided cumulatively for each of the following parameters and categories:

- HDL:
 - <=LLN
 - <0.8x LLN
- LDL, cholesterol, triglycerides:
 - >=ULN
 - >1.5 x ULN
 - > 2.5 x ULN

Newly occurring or worsening liver enzyme abnormalities will also be summarized based on the event criteria given in Table 2-5:

Table 2-5 Liver-related events

| Parameter | Criterion |
|------------------------|--|
| ALT | >3xULN; >5xULN; >8xULN;>10xULN, >20xULN |
| AST | >3xULN; >5xULN; >8xULN >10xULN; >20xULN |
| ALT or AST | >3xULN; >5xULN; >8xULN >10xULN; >20xULN |
| TBL | >1.5xULN; >2xULN; >3xULN |
| ALP | >2xULN; >3xULN; >5xULN |
| ALT or AST & TBL | ALT or AST>3xULN & TBL >2xULN; ALT or AST >5xULN & TBL >2xULN; ALT or AST >8xULN & TBL >2xULN; ALT or AST >10xULN & TBL >2xULN; |
| ALP & TBL | ALP >3xULN & TBL >2xULN ALP >5xULN & TBL >2xULN |
| ALT or AST & TBL & ALP | ALT or AST>3xULN & TBL >2xULN & ALP <2xULN (Potential Hy's Law) |

| Parameter | Criterion |
|---|-----------|
| Note: elevated ALP may suggest obstruction as a consequence of gall bladder or bile duct disease; ALP may also be increased in malignancy. FDA therefore terms Hy's Law cases as indicators of pure hepatocellular injury. This does not mean that cases of ALT or AST >3xULN & TBL >2xULN & ALP ≥ 2xULN may not result in severe DILI. | |
| Notes: | |
| 1) In studies which enroll subjects with pre-existing liver disease, baseline LFT may be increased above ULN; in such a case it is meaningful to add the condition "and worse than baseline" to the abnormality criteria | |

For a combined criterion to be fulfilled, all conditions have to be fulfilled on the same visit. The criteria are not mutually exclusive, e.g. a subject with ALT = 6.42xULN is counted for ALT > 3xULN and ALT>5x ULN.

Individual subject data listing may be provided for subjects with abnormal laboratory data. Data of subjects with newly occurring or worsening liver enzyme abnormalities may be listed in an additional listing.

The laboratory values below Lower Level of Quantification (LLQ) or above Upper Level of Quantification (ULQ) will be imputed as LLQ or ULQ, respectively. The numerical part of the reported result will be treated as the actual LLQ or ULQ.

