## 1.2 Purpose

The purpose of this bridging study is to evaluate efficacy, safety and tolerability of secukinumab 150 mg s.c. compared to placebo in Chinese participants with active nr-axSpA at Week 16 to support registration in China. Meanwhile, this study will also observe the long-term efficacy, safety and tolerability of secukinumab including spinal and SI-joint inflammation as evidenced by magnetic resonance imaging (MRI) at Week 52.

Additionally, efficacy, safety and tolerability of secukinumab 300 mg s.c. will be assessed in non-responders, defined as participants who have not achieved ASAS20 at Week 24.

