2.1.1.3 Screening, baseline and post-baseline definitions

Screening refers to any procedures (e.g., checking inclusion and exclusion criteria) performed prior to the date of first dose of study treatment. Per protocol, subject informed consent must be obtained prior to performing any study related activity. The date of signing informed consent is the start date of screening period. Any assessment obtained during the screening period will be labeled screening assessment. Assessments made on Day 1 may occur before or after the randomization or the first dose. Further information will be found in Programming Datasets Specifications (PDS).

In general, a baseline value refers to the last measurement made prior to administration of the first dose of study treatment. A post-baseline value refers to a measurement taken after the first dose of study treatment. However, for vital sign, laboratory assessments and ECG if no pre-treatment value exists, values obtained after first dose of treatment can be used as baseline only if it was collected on the same day as first dose.

Of note, baseline will be derived based on the first dose day while exact dosing time is not considered.

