| Post-baseline safety | Summary visit information (e.g. lab, ECG, etc.) | 
For visits without switch of treatment in the window, the measurement closest to the target will be used. In the event two measurements are taken equally apart (e.g. 1 before target date and 1 after) the first one will be used.
 
For visits during which the patient switches from placebo to AIN the following will be done based on whether the patient met the rescue criteria:
 
 a. if the analysis visit window is <= week 16, then 
 - if available, the closest measurement to the target date which is ON or BEFORE the switch date will be used (i.e. the closest measurement to target which is on placebo) - if there are no data on or before the switch then the closest measurement to the target date after the switch will be used b. if the analysis visit window is > week 16, then 
 - if available, the closest measurement to the target date which is AFTER the switch date will be used (i.e. the closest measurement to target which is on AIN) - if there are no data AFTER the switch then the closest measurement to the target date before the switch will be used 
Cases where the same parameter is recorded more than once on the same date will be handled as follows:
 
 * if time of completion exists and differs, the earliest measurement will be used; * if time of completion is the same, the measurements will be averaged; * if time does not exist the measurement from the lowest CRF visit number will be used. |
| Post-baseline safety | Notable abnormalities (e.g. lab) | The most extreme measurement in the window will be used. Note this means a patient can have a notably high and notably low measurement within a window. |

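### SAP Table 2-2 puts no treatment-switch condition on notable abnormalities, so a value taken on open-label secukinumab can stand as a placebo participant's Week 16 notable value

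*SAP*

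**What the plan says.** SAP Section 2.4.1.2, Table 2-2, sets which value represents a participant when several fall in one visit window. Its two post-baseline safety rows differ:

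- **By-visit summaries.** Where a participant moves from placebo to secukinumab, windows up to Week 16 take the value nearest the target day on or before the switch. A post-switch value is used only if there is no earlier one.
- **Notable abnormalities.** "The most extreme measurement in the window will be used". Nothing is said about a switch.

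SAP Section 2.4.1.1, Table 2-1, gives the Week 16 windows (target Day 113): Days 100–155 for hematology, chemistry and urinalysis, Days 86–239 for lipids, and Days 2–239 for weight and ECG. Repeat and unscheduled visits are mapped in the same way as scheduled ones. The analysis visit also decides the visit and period under which safety data are listed.

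On baseline, SAP 2.1.1.3 says: "In general, a baseline value refers to the last measurement made prior to administration of the first dose of study treatment". SAP 2.7.3 plans CTCAE shift tables against the worst result "during the treatment phase (either initial up to week 16 or entire) analyzed", and adds: "Of note, baseline will be defined as last assessment prior to first dosing in initial treatment phase". It then plans two further outputs: "Summaries for newly occurring or worsening clinically notable lipid abnormalities will also be provided cumulatively", and "Newly occurring or worsening liver enzyme abnormalities will also be summarized based on the event criteria". Neither names the value against which new or worse is judged.

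On columns, SAP 2.1.1.1 summarizes by randomized treatment or by treatment sequence. It allows some safety summaries to separate the switch treatments: "Entire study: Any AIN457 150 mg, Any AIN457 300 mg, Any AIN457, Placebo".

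**The concern.** All placebo participants move to open-label 150 mg at Week 16, and ASAS20 non-responders move to 300 mg at Week 24. A laboratory rule that ignores these dates can credit a value to the wrong treatment.

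For the notable-abnormality row the direction matters. A value that arose on secukinumab would be added to the placebo column at Week 16, which narrows the safety contrast in the only placebo-controlled period.

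The fixed baseline raises a separate question about the entire-study tables. Protocol 1.2 states that "efficacy, safety and tolerability of secukinumab 300 mg s.c. will be assessed in non-responders". A 300 mg column that also holds abnormalities already present on 150 mg, or on placebo, does not show what arose on 300 mg.

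**Working it through.** The documents state no figure on this point, so there is none to reproduce.

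**1. How far the Week 16 windows run past the switch (SAP Table 2-1).**
- Hematology and chemistry: 155 − 113 = 42 days.
- Lipids and ECG: 239 − 113 = 126 days. These windows also pass the Week 24 escalation (Day 169) by 239 − 169 = 70 days, so they can hold values on 300 mg.

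**2. Which samples can fall there.**
- *Routine samples: none.* Week 16 assessments precede the first open-label dose (SAP 1.1, Protocol 6.7.2). The next hematology and chemistry window is Week 24 (target Day 169, opening on Day 156). The next for lipids and ECG is Week 52.
- *Unscheduled or repeat samples:* any taken in those 42 or 126 days.
- *Early end-of-treatment visits:* Protocol 8 and 9.1.1 place these 4 weeks after the last dose, so visit day = last-dose day + 28. This assumes that the visit falls on its nominal day and carries the Week 52 assessments.

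| Last dose | Visit day | In hematology/chemistry Week 16 window (to 155)? | In lipid/ECG Week 16 window (to 239)? |
|---|---|---|---|
| Week 16, Day 113 | 141 | Yes | Yes |
| Week 20, Day 141 | 169 | No | Yes |
| Week 24, Day 169 | 197 | No | Yes |
| Week 28, Day 197 | 225 | No | Yes |
| Week 32, Day 225 | 253 | No | No |

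**3. The two rows applied to one invented case.** A placebo participant has a normal ALT before dosing on Day 113 and an ALT above 3×ULN in an unscheduled sample on Day 130. Both values fall in the Week 16 window. The by-visit row selects Day 113, on placebo. The notable-abnormality row selects Day 130, on secukinumab.

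**4. Fixed baseline, if the switch-treatment columns are used.** Let p be the share with an abnormality arising before the switch, and f the share of those still meeting the criterion after it. Both are assumptions: p = 2–10%, f = 25–100%. With 134 randomized 1:1 there are about 67 placebo starters, and all are assumed to switch.

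- Carried-over count = 67 × p × f. Added points in Any AIN457 = 100 × count / 134.
- Low: 67 × 0.02 × 0.25 = 0.34 participants; 0.25 points.
- High: 67 × 0.10 × 1.00 = 6.7 participants; 5.0 points.
- For the 300 mg column, assume that 20–40% of 134 escalate (26.8 to 53.6 participants). Low: 26.8 × 0.02 × 0.25 = 0.13. High: 53.6 × 0.10 × 1.00 = 5.4. As a share of that column, this is 0.5 to 10 points.
- A carry-over from 150 mg to 300 mg adds nothing to Any AIN457, where the participant is counted once.
- By randomized group or treatment sequence each participant appears once, so the double count is zero.

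**The case against.** **On the windows.** No scheduled post-switch sample falls in the Week 16 windows, so 42 and 126 days measure the opening and not the number of values affected. The CTCAE worst-grade tables are defined by treatment phase and not by visit window. This stands and limits the size. It does not remove the gap: unscheduled repeats may be follow-up of an abnormal result, and the adjacent row shows that the SAP saw a need for a switch rule.

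**On the baseline.** A reader might infer that placebo-onset abnormalities will be counted again as new on secukinumab, and those from 150 mg again on 300 mg. The documents do not support that:

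- The quoted baseline sentence governs the CTCAE shift tables. For the lipid and liver summaries the pre-first-dose value is the likely default, but the text does not say so.
- The switch-treatment columns are optional, and no text assigns them to laboratory tables. Table 2-3 plans only crude incidence for notables.
- A contrast with adverse events does not help. Treatment-emergent events are also counted from the first dose of study treatment (SAP 2.7.1), and Table 5-3 illustrates exposure time for two separate events, not one event that persists across a switch.

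**On re-anchoring.** The pre-first-dose baseline is stated deliberately, and safety is descriptive. Replacing it could hide an abnormality that began on 150 mg and continued on 300 mg. This is a fair reason to keep the original tables and only add to them.

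**Conclusion.** The notable-abnormality row of Table 2-2 lacks the switch condition that its neighbor has. As written, it allows a value on secukinumab to stand as a placebo participant's Week 16 notable value. The route is limited to unscheduled samples and to end-of-treatment visits of participants who stop soon after the switch. The number of cases is therefore likely small, and the documents do not allow a count.

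The fixed baseline is a secondary and conditional point. It has an effect only if entire-study laboratory tables use the optional columns and the abnormality persists past the switch. The range of about 0.3 to 6.7 participants (0.25 to 5 points in Any AIN457) rests wholly on assumed rates. The fixed baseline does not affect the Day 1 to Week 16 comparison.

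**What to change.** 1. **Table 2-2, notable abnormalities.** For windows up to Week 16, limit the most extreme value to samples on or before the first open-label dose, and assign later values to the treatment then being taken. Do not carry over the by-visit row's fallback to a post-switch value, which would reopen the gap. The cost is a sentence and one programming condition, with essentially no downside.
2. **SAP 2.7.3, reference and columns.** State the reference value for the lipid and liver summaries of new or worsening abnormalities, and which treatment grouping the entire-period laboratory tables use.
3. **SAP 2.7.3, only if the switch-treatment columns are used.** Keep the original-baseline tables. Add a supplementary count of abnormalities not already present at the last value before the first dose of that column's treatment. This needs a second baseline flag and no new data; where no sample was taken at the switch, use the last earlier value.
4. **Limit to state for lipids.** Table 2-1 has no Week 24 lipid window, so routine samples cannot separate the step from 150 mg to 300 mg. The supplementary 300 mg count for lipids should say so.
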